### Physiological Measures

1. **Alcohol Breath Testing:** Alcohol breath testing will be performed at every study visit.
2. **Medical History and Physical Exam:** A comprehensive medical history and physical examination will be performed on all participants during the screening process.
3. **Pregnancy Testing:** Serum pregnancy testing will be performed during screening and a urine pregnancy test will be performed at study weeks 4 and 8.
4. **Serum laboratory examination:** Complete blood count, electrolytes, and liver function tests will be performed during the screening process.
5. **Urinalysis:** Laboratory urinalysis (glucose, protein, ketones, pH, specific gravity, microscopic analysis) will be performed during the screening process.
6. **Urine Toxicology:** Urine samples for toxicology will be collected under directly observed conditions during screening and study weeks 4 and 8 to detect any non-alcohol substance use.
7. **Vital Signs:** Temperature, pulse, and blood pressure will be measured at every study visit for data collection and safety monitoring purposes.

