## **Blood and other Biological Samples**

Please create or insert a table describing the proposed collection of blood or other biological specimens

Approximately 20 ml of blood (4 teaspoons) will be drawn at the time of baseline assessment for routine analyses including complete blood count, electrolytes, liver function tests, and blood pregnancy test for women. They may be repeated during the study if clinically indicated.

***Urinalysis:*** Laboratory urinalysis (glucose, protein, ketones, pH, specific gravity, microscopic analysis) will be performed during the screening process.

***Urine Toxicology:*** Urine samples for toxicology will be collected under directly observed conditions during screening and study weeks 4 and 8 to detect any non-alcohol substance use.

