### **Research Related Delay to Treatment**

Will research procedures result in a delay to treatment?

Yes

Maximum duration of delay to any treatment

Once screening is completed, there is no delay for study entry for eligible patients.

The patient should receive treatment medication within 2-3 weeks after the initial screening evaluation.

Medical management therapy is an abstinence-focused supportive psychotherapy condition developed for substance use disorder pharmacotherapy clinical trials and will begin in week 1 of the treatment study.

Medical management therapy approximates the level of support of abstinence that patients would expect to receive in community treatment (general support of abstinence, tying improvement to reduction or cessation of drug use, referral to 12-step programs, etc.)

Maximum duration of delay to standard care or treatment of known efficacy

Because the screening procedure sometimes requires 2-3 meetings, individuals may not begin medical management therapy until 2-3 weeks after their initial screening evaluation for the study. Medical management therapy will start during week 1 of the treatment study.

Treatment to be provided at the end of the study

At the conclusion of the 9-week protocol, the participants will be offered supportive therapy for at least one additional month or until an appropriate referral for on-going treatment is made.

If a patient found the medication to be beneficial, they will be given an appropriate referral for ongoing treatment.

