## **Risks/Discomforts/Inconveniences**

### Risks that could be encountered during the study period

The major risk of research participation is related to drug administration. Pregabalin will be administered up to a maximum of 600mg per day. Side effects most commonly associated with pregabalin include: drowsiness, dizziness, dry mouth, constipation, difficulty concentrating, swollen arms/legs, and weight gain. Some serious side effects, which are unlikely, include: blurred vision, unusual bleeding/bruising, unsteadiness, confusion, muscle pain/tenderness/weakness, swelling of hands/legs/feet, signs of kidney problems (such as change in the amount of urine). Rare side effects include: rash, itchiness, trouble breathing, and changes in a participant's mood, thoughts, or behavior such as depression or suicidal ideation. All participants are fully informed of the side effect that they might experience.

Participants may be at greater risk if they self-administer other drugs that interact with the study medications. To the extent that they do not reduce or eliminate alcohol use, risk may increase. It is not considered safe during pregnancy or breast-feeding. Therefore, female participants will be required to use adequate methods of birth control. Serum pregnancy will be completed at baseline and urine pregnancy tests will be evaluated at week 4 and 8. If a female patient becomes pregnant, she will be withdrawn from study

---

medication and offered continuing non-pharmacological treatment (i.e., psychotherapy) with STARS until the conclusion of treatment or given referrals to other treatment centers.

The structured interviews, rating scales, and questionnaires should add no physical risk. However, because many of the interviews and assessments are time-consuming to complete and involve topics of a sensitive nature, some people have found them to be physically or emotionally tiring. All participants will be informed that they can refuse to complete anything they are uncomfortable completing.

Participants will complete a blood draw at screening which can cause slight discomfort and bruising. They will be warned prior to completion of these facts.

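### The protocol text schedules one pregnancy test before treatment, on a day it does not fix, and none again until week 4, so the negative result behind exclusion 6 can be up to about 21 days old at first dose

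*Protocol*

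**What the plan says.** Pregnancy is exclusion 6 in the protocol's Inclusion/Exclusion Criteria, ascertained by medical history and serum HCG. The same criterion excludes women who do not use adequate contraception. Pregnancy during the study is a drop-out criterion (Criteria for Early Discontinuation), and the risk section says of the drug: "It is not considered safe during pregnancy or breast-feeding".

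The test schedule appears in three places:

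- Physiological Measures, item 3: "Serum pregnancy testing will be performed during screening and a urine pregnancy test will be performed at study weeks 4 and 8".
- Risks that could be encountered during the study period: "Serum pregnancy will be completed at baseline and urine pregnancy tests will be evaluated at week 4 and 8".
- Blood and other Biological Samples: about 20 ml of blood "will be drawn at the time of baseline assessment for routine analyses". The list that follows includes the pregnancy test for women. The section adds: "They may be repeated during the study if clinically indicated".

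On timing, Research Related Delay to Treatment says: "The patient should receive treatment medication within 2-3 weeks after the initial screening evaluation". It also says that screening sometimes takes two or three meetings, and that eligible patients enter without delay once screening is finished. Under Study Procedures, the upward titration takes three weeks, to 600 mg per day or the highest dose tolerated.

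The SAP does not mention pregnancy testing.

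**The concern.** An eligibility criterion matters most when exposure begins. Here the only scheduled evidence on pregnancy before dosing is one serum result whose date is left open. Two sections say baseline and one says screening, so staff could draw the blood at the first screening meeting or on the day of entry and believe in either case that they had followed the protocol. With an early draw, a pregnancy can begin after the negative result and before the first bottle is dispensed. The next scheduled test comes only after the titration is over. What is at stake is fetal exposure to a drug that the protocol itself says is unsafe in pregnancy.

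**Working it through.** **Step 1. When is the serum test done?** The risk section uses both terms. It puts the serum pregnancy test at baseline, yet also says: "Participants will complete a blood draw at screening which can cause slight discomfort and bruising". Physiological Measures lists the same routine blood tests under screening, and the section on minimizing risks also places the blood sample there. The likeliest reading is one draw, during screening, which some sections call baseline. No section gives its day.

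**Step 2. Inputs.**

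| Quantity | Value | Source |
|---|---|---|
| Initial screening evaluation to first dose | up to 2-3 weeks, so at most about 21 days | Research Related Delay to Treatment |
| End of screening to entry | no delay, taken as 0 days | same section |
| First test on treatment | week 4 | Physiological Measures |
| Titration | 3 weeks = days 1-21 | Study Procedures |
| Women | 20% of 20 | Description of Subject Population |

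Assumptions: dosing starts on study day 1, and week 4 is days 22-28.

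**Step 3. Age of the negative result at first dose.** 0 days if drawn at entry, about 21 days if drawn at the initial evaluation after the longest screening.

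**Step 4. Drug received before the week-4 test.** 22 − 1 = 21 days to 28 − 1 = 27 days. All 21 days of titration fall inside this.

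**Step 5. Gap between the two tests** = age of result + days on drug.

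- Draw at entry: 0 + 21 to 0 + 27 = 21-27 days.
- Draw at the initial evaluation, upper limit: 21 + 27 = 48 days.

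**Step 6. Conception after dosing starts.** Exposure in pregnancy up to the week-4 test is (21 to 27) minus the day of conception:

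- day 1: 20-26 days
- day 7: 14-20 days
- day 14: 7-13 days
- day 20: 1-7 days

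**Step 7. Women affected.** 0.20 × 20 = 4 expected. The chance of enrolling at least one woman is 1 − 0.8^20 = 0.9885. Since the age range is 18-65, the number able to conceive is 4 or fewer.

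**Step 8. What a test at the first visit would find.** The documents give no detection lag. Assume a test turns positive L = 7 to 14 days after conception, and that conceptions are spread evenly over the g days from draw to first dose. The share of these found is (g − L)/g:

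- L = 7: 7/14 = 50% for g = 14, and 14/21 = 67% for g = 21.
- L = 14: 0/14 = 0% for g = 14, and 7/21 = 33% for g = 21.

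The test would also find conceptions in the L days before the draw that the serum test was too early to detect. If both tests have the same lag, the share found of all conceptions missed before first dose is g/(g + L). This runs from 14/28 = 50% to 21/28 = 75%. If g = 0, the extra test adds nothing.

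**The case against.** The strongest reply is that the visible text is incomplete. The schedule of study assessments is an attachment whose content is not shown, and screening runs under a separate umbrella protocol (6582R). Either could fix the day of the draw or include a test at the first visit. This stands as a limit: a reader might infer that no first-dose test exists, but the documents show only that the protocol text schedules none. If the attachment does list one, Physiological Measures and the risk section would still need to be aligned with it, since each sets out the test times without it.

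The reply can also point to safeguards. Adequate contraception is required, blood tests may be repeated if indicated, visits are frequent in the first two weeks, and a woman who becomes pregnant is taken off study medication. These lower the risk. They do not supply a scheduled check, and an unrecognized early pregnancy may give no reason to repeat a test.

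Three stronger readings are tempting and do not hold:

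- *Any conception after the draw means three weeks or more of undetected exposure.* Step 6 shows that, counted to week 4, a conception after dosing starts mostly gives less. One too recent to show at week 4 could run on to the week-8 test, but a first-visit test would find neither.
- *The gap between tests is at least 35 days (14 + 21) for an early draw.* The 2-3 weeks is a ceiling on the delay, so 14 days is not a minimum.
- *The dose and tolerability results would contain an ineligible participant.* A woman who conceives after entry was eligible when she entered and meets a drop-out criterion. No effect on the summaries has been shown.

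**Conclusion.** The point holds as a modest, specific safety gap. As the protocol text stands, the pregnancy result used for eligibility can be 0 to about 21 days old at first dose. A conception between the draw and first dose, or just before the draw, can be followed by 21-27 days of drug, including the full titration, before the next scheduled test. The gap between tests runs from 21-27 days with a draw at entry to at most about 48 days. That maximum combines the earliest draw, the longest screening and the last day of week 4.

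The conclusion rests on reading baseline as the screening draw, on dosing from day 1, and on the attached schedule adding no test. It concerns about 4 women at most on the planned sex distribution. It changes no estimate, test or sample size in the protocol or SAP.

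**What to change.** 1. Reconcile Blood and other Biological Samples, Physiological Measures item 3, the risk section and the attached schedule of assessments. Use one term for the serum test's timing, and state when in screening the blood is drawn relative to first dose.
2. In Physiological Measures and the risk section, add the urine pregnancy test already used at weeks 4 and 8 to the first study visit, so that exclusion 6 is ascertained with a current result at study entry.

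The cost is about 4 or fewer extra urine tests at a visit already scheduled, plus a sentence in each section. With an early draw, the longest interval without a test before week 4 falls from at most about 48 days to 21-27 days. Very recent conceptions would still be missed, and conception after dosing starts still depends on contraception, clinical prompts and the tests at weeks 4 and 8.

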### Interviews

1. **Alcohol Timeline Follow-Back (TLFB-A):** The alcohol timeline Followback method (Litten and Allen 1992) will gather self-reported alcohol use data.
2. **Clinical Global Impression Scale-Observer (CGI):** The CGI-Severity and -Improvement scales (Guy 1976) will be used to measure the overall clinical status of the subject and change from baseline.
3. **Clinical Institute Withdrawal Assessment-Alcohol (CIWA-Ar):** The CIWA-Ar (Sullivan et al. 1989), a 10-item scale, is the most widely-used measure of alcohol withdrawal symptoms.
4. **Hamilton Anxiety Scale (HAMA):** The HAM-A (Hamilton 1959) is a 14-item instrument widely used to measure current anxiety symptoms.
5. **SAFTEE:** The Systematic Assessment for Treatment and Emergent Events (SAFTEE) modified for the COMBINE study (Johnson et al. 2005) will be performed at each study visit.
6. **Psychiatric Evaluation and Diagnosis:** The MINI International Neuropsychiatric Interview will be performed during screening as part of a complete psychiatric diagnostic assessment.
7. **Structured Pill Count Interview:** The Structured Pill Count Interview is a Timeline Follow-Back assessment of study medication compliance accounting for each dose of prescribed study medication.
8. **Modified Treatment Services Review (TSR):** The Modified Treatment Services Review is an 18-item questionnaire modified from the Treatment Services Review (McLellan et al. 1992) that assesses the past week exposure of the subject to health care and substance use disorder treatment.

### Self-Report

1. **Clinical Global Impression-Self (CGI-S):** The CGI-Self is a 2-item scale that asks the subject to rate their current level of symptoms and change from baseline (Ecdeu 1976).
2. **Medical Outcomes Study Sleep Measure (MOS):** A 12-item measure for characterizing the quality of sleep (Hays et al. 2005).
3. **Obsessive Compulsive Drinking Scale (OCDS):** A 14-item questionnaire that assesses aspects of alcohol craving (Anton et al. 1995).

---

Please attach copies, unless standard instruments are used  
schedule of study assessments 4-18-17.pdf

### **Off label and investigational use of drugs/devices**

Choose from the following that will be applicable to your study

Drug

Select the number of drugs used in this study

1

#### **Drug #1**

Name of the drug

Pregabalin

Manufacturer and other information

Other name: Lyrica

Manufacturer: Pfizer

The generic Pregabalin is manufactured by 20 companies.

Please note there are currently 66 brands of generics of Pregabalin.

Approval Status

No IND is required

Choose one of the following options

FDA has determined that IND is not required

### **Research Related Delay to Treatment**

Will research procedures result in a delay to treatment?

Yes

Maximum duration of delay to any treatment

Once screening is completed, there is no delay for study entry for eligible patients.

The patient should receive treatment medication within 2-3 weeks after the initial screening evaluation.

Medical management therapy is an abstinence-focused supportive psychotherapy condition developed for substance use disorder pharmacotherapy clinical trials and will begin in week 1 of the treatment study.

Medical management therapy approximates the level of support of abstinence that patients would expect to receive in community treatment (general support of abstinence, tying improvement to reduction or cessation of drug use, referral to 12-step programs, etc.)

Maximum duration of delay to standard care or treatment of known efficacy

Because the screening procedure sometimes requires 2-3 meetings, individuals may not begin medical management therapy until 2-3 weeks after their initial screening evaluation for the study. Medical management therapy will start during week 1 of the treatment study.

Treatment to be provided at the end of the study

At the conclusion of the 9-week protocol, the participants will be offered supportive therapy for at least one additional month or until an appropriate referral for on-going treatment is made.

If a patient found the medication to be beneficial, they will be given an appropriate referral for ongoing treatment.

## **Clinical Treatment Alternatives**

### Clinical treatment alternatives

Participants will be informed of alternatives to participation in the proposed trial. The alternative procedures available are individual counseling by other clinicians, 12-step facilitation, or more intensive treatment for heavy drinking such as inpatient or outpatient detoxification, inpatient rehabilitation, or intensive outpatient programs. Additionally there are a number of medication that may aid in relapse prevention, including naltrexone (Revia) and disulfiram (Antabuse). Patients are informed that they may request referral for other treatment options. In addition, participants may withdraw from this study at any time and request referrals for other treatment options.

## **Risks/Discomforts/Inconveniences**

### Risks that could be encountered during the study period

The major risk of research participation is related to drug administration. Pregabalin will be administered up to a maximum of 600mg per day. Side effects most commonly associated with pregabalin include: drowsiness, dizziness, dry mouth, constipation, difficulty concentrating, swollen arms/legs, and weight gain. Some serious side effects, which are unlikely, include: blurred vision, unusual bleeding/bruising, unsteadiness, confusion, muscle pain/tenderness/weakness, swelling of hands/legs/feet, signs of kidney problems (such as change in the amount of urine). Rare side effects include: rash, itchiness, trouble breathing, and changes in a participant's mood, thoughts, or behavior such as depression or suicidal ideation. All participants are fully informed of the side effect that they might experience.

Participants may be at greater risk if they self-administer other drugs that interact with the study medications. To the extent that they do not reduce or eliminate alcohol use, risk may increase. It is not considered safe during pregnancy or breast-feeding. Therefore, female participants will be required to use adequate methods of birth control. Serum pregnancy will be completed at baseline and urine pregnancy tests will be evaluated at week 4 and 8. If a female patient becomes pregnant, she will be withdrawn from study

---

medication and offered continuing non-pharmacological treatment (i.e., psychotherapy) with STARS until the conclusion of treatment or given referrals to other treatment centers.

The structured interviews, rating scales, and questionnaires should add no physical risk. However, because many of the interviews and assessments are time-consuming to complete and involve topics of a sensitive nature, some people have found them to be physically or emotionally tiring. All participants will be informed that they can refuse to complete anything they are uncomfortable completing.

Participants will complete a blood draw at screening which can cause slight discomfort and bruising. They will be warned prior to completion of these facts.

#### Describe procedures for minimizing risks

Participants are carefully screened for psychiatric risk prior to admission, so we anticipate the risk of clinically-significant psychological deterioration during participation to be low. The exclusion criteria are designed to minimize the medical and psychiatric risks to participants as discussed above, including risks of adverse events and side effects. All patients will be informed of the possible side effects and risks through extensive discussions with the research psychiatrist during the consent process.

Alcohol withdrawal will be assessed at each study visit using the Clinical Institute Withdrawal Alcohol (CIWA-AR). Anxiety and drinking will be assessed weekly.

Participants will provide a blood sample during screening; they will be warned that blood drawing may cause slight discomfort at the site of needle entry and may result in a small bruise.

Patients are informed prior to study entry that they can refuse to answer any questions and that they can request to stop at any time. If a participant becomes agitated during any of the interviews or assessments, he or she will be provided with therapeutic assistance.

#### Methods to Protect Confidentiality

##### Describe methods to protect confidentiality

A Certificate of Confidentiality will be acquired for this study from the National Institute on Drug Abuse to offer protection for the privacy of participants by protecting identifiable research information from forced disclosure (e.g., through a subpoena or court order). The Certificate of Confidentiality will allow investigators and others with access to research records to refuse to disclose information that could identify participants in any civil, criminal, administrative, legislative, or other proceeding, whether at the Federal, State, or local level. The Certificate of Confidentiality is granted for studies that collect information that, if disclosed, could damage participants' financial, employability, insurability, or reputation, or have other adverse consequences.

We use coded records (i.e. initials and numbers), store signed consent forms in a locked safe, and try, to the best of our ability to maintain confidentiality. Only coded records will be entered into the computer and the security of electronic data is ensured at the level of the server, the user, and the database. We do, however, point out to prospective patients, that we cannot assure that their drug histories and other personal records might not become known.

*Will the study be conducted under a certificate of confidentiality?*

---

Yes, we will apply for the Certificate of Confidentiality

## **Direct Benefits to Subjects**

### Direct Benefits to Subjects

In addition to the experimental treatment of pregabalin, all participants will receive Medical Management, a supportive behavioral treatment of established efficacy. Participants will also receive up to an additional four weeks of free treatment for AUD following the end of the study period.

